#### **5.8.3. Vital Signs**

For vital sign parameters (systolic blood pressure, diastolic blood pressure, heart rate, respiratory rate, body temperature, and weight) the observed values and change from baseline will be summarized using descriptive statistics at each visit. The maximum post-baseline values and the change from baseline by visit will also be summarized.

A listing of all vital sign data will be provided.

#### **5.8.4. KPS**

The observed values and the change from baseline in the KPS will be summarized using descriptive statistics at each visit. The maximum post-baseline values and the change from baseline by visit will also be summarized.

A listing of KPS data will be generated.

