7. KPS  $\geq 70$  at screening and baseline.
8. Undergone prior vaccination against PV and received a boost immunization with trivalent IPOL® (Sanofi-Pasteur SA) at least 1 week, but less than 6 weeks, prior to administration of PVSRIPO (within 6 months of PVSRIPO retreatment). Note: Patients who are unsure of their prior vaccination status/who have not been vaccinated must provide proof of vaccination and/or evidence of anti-PV immunity prior to enrollment, as applicable.
9. Ability to safely discontinue anti-coagulant therapy(ies) prior to biopsy/catheter placement, as required per site/surgical guidelines, in the opinion of the investigator.
10. Hemoglobin  $\geq 9$  g/dL prior to biopsy/catheter placement.
11. Platelet count  $\geq 100,000/\mu\text{L}$  (unsupported);  $\geq 125,000/\mu\text{L}$  (can be supported via platelet transfusion) at biopsy/catheter placement and/or with a Sponsor-approved bone marrow stimulant/colony stimulating factor, eg, romiplostim).
12. ANC  $\geq 1000/\mu\text{L}$  prior to biopsy/catheter placement.
13. Creatinine  $\leq 1.2 \times \text{ULN}$  prior to biopsy/catheter placement.
14. Total bilirubin, ALT, AST, ALP  $\leq 2.5 \times \text{ULN}$  prior to biopsy/catheter placement.
15. PT and aPTT  $\leq 1.2 \times \text{ULN}$  prior to biopsy/catheter placement.
16. If undetectable ATT IgG at screen, Tdap booster vaccine  $> 1$  week prior to biopsy/catheter placement.
17. Patients must be willing and able to understand and provide written informed consent.

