### **3.2.5. Presentations by Worst Case**

When data are collected serially over time, individual data presentations may include “worst case on study” displays. In those situations, both scheduled and unscheduled assessments up to 104 weeks will be included.

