### **5.1. PARTICIPANT DISPOSITION, DEMOGRAPHIC AND BASELINE CHARACTERISTICS**

Participant disposition will be presented for the screening analysis set. A summary table will be generated for the overall population. The number of participants who were screened, screen failures, and the reason for screen failure will be summarized. Additionally, the number of participants in each analysis population will be summarized. The end of treatment status including reasons for treatment discontinuation, as well as end of study status including reasons for study discontinuation reason will be provided. Similarly, the death status and primary reason for death will be presented. The number of days on study will also be summarized. Participant disposition including analysis population, end of treatment status and reason, end of study status and reason, and death status (including date of death) and reason will be listed.

Demographic data and baseline characteristics including age at informed consent, gender, race, ethnicity, Karnofsky performance status (KPS) at baseline, and baseline height, and weight will be summarized using descriptive statistics. Frequency of KPS scores < 70, 70, 80, 90, and 100 will be summarized for the safety population set. Demographic data and baseline characteristics will be listed.

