### **5.8. SAFETY**

Values for all safety variables will be listed by participant and visit (as applicable). Safety summaries by visit will use scheduled visits up to Week 104.

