### 5.8.2. Clinical Laboratory Assessments

AEs for clinical labs will be characterized according to CTCAE version 5 (when possible) and shift in grade from baseline to the worst post-baseline value will be summarized. Both scheduled and unscheduled assessments will be used to identify the worst post-baseline values.

The following categories of abnormal hepatic laboratory values will be evaluated for any occurrence among all post baseline assessments.

- Alanine Aminotransferase (ALT) and/or Aspartate Aminotransferase (AST)  $> 3 \times$  upper limit normal (ULN), Alkaline Phosphatase (ALP)  $< 2 \times$  ULN, and Total Bilirubin  $\geq 2 \times$  ULN

- AST > 3, 5, 8, 10, and 20 x ULN, and 5 x ULN for more than 5 weeks
- ALT > 3, 5, 8, 10, and 20 x ULN, and 5 x ULN for more than 5 weeks
- Total Bilirubin > 1.5 or  $\geq 2$  x ULN

Listings of all laboratory data with normal reference ranges, and CTCAE grades (when possible) will be provided.

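### SAP 5.8.4 summarises the maximum post-baseline KPS, which is each patient's best score, and plans no per-patient worst score

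*SAP*

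**What the plan says.** SAP 5.8.4 plans two things for KPS besides a listing. The first is by visit: "The observed values and the change from baseline in the KPS will be summarized using descriptive statistics at each visit". The second is "The maximum post-baseline values and the change from baseline by visit will also be summarized". That second sentence also appears, word for word, in SAP 5.8.3 for vital signs.

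The laboratory section, SAP 5.8.2, takes the opposite approach to extremes: "Both scheduled and unscheduled assessments will be used to identify the worst post-baseline values". SAP 3.2.5 is a general provision under which "individual data presentations may include “worst case on study” displays", and for such displays "both scheduled and unscheduled assessments up to 104 weeks will be included". It does not mention KPS.

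SAP 5.8 adds that "Safety summaries by visit will use scheduled visits up to Week 104". Section 10 of the SAP lists one KPS table, 14.3.4.5, which is by visit. Protocol 8.4.5 places KPS change over time among the safety results to be reported.

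**The concern.** A per-patient extreme in a safety section is there to show how bad things became for each patient. For blood pressure or temperature a high value can be the worrying one, so a maximum makes sense. For KPS it is the reverse. The maximum records the best the patient ever was after infusion, and nothing in the SAP explains why that would be wanted.

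The gap matters because the expected toxicity here is neurologic. Protocol 7.4 makes neurologic events from peritumoral or cerebral edema the main focus of dose-limiting toxicity, and SAP 3.2.6 names both kinds of edema as events of special interest. SAP Section 6 drops patient-reported outcomes and progression-free survival. KPS and the NANO scale are therefore the main functional measures left, and SAP 5.8.5 plans no worst-case display for NANO either.

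**Working it through.** The plan states no figure for this point, so there is none to reproduce. The check is on direction, and then on what the planned tables can and cannot show.

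**Step 1: direction of the scale.** The documents do not say in words that high KPS is good, but they treat it so. Protocol 4.1, criterion 7, sets a floor of 70 "at screening and baseline", and SAP 5.1 plans baseline categories as follows: "Frequency of KPS scores < 70, 70, 80, 90, and 100 will be summarized for the safety population set". The maximum is therefore the best score.

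**Step 2: which maximum.** SAP Section 5 already includes the minimum and maximum across patients in its descriptive statistics, so the natural reading of the extra sentence is a per-patient maximum. If it means the maximum across patients, it duplicates what is already there. Neither reading yields a per-patient worst score.

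**Step 3: what the maximum distinguishes.** Four invented patients:

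| Patient | Baseline | Post-baseline scores | Maximum | Minimum | Minimum − baseline |
|---|---|---|---|---|---|
| A, declines | 90 | 90, 80, 80, 70, 60, 50 | 90 | 50 | −40 |
| B, stable | 90 | 90 throughout | 90 | 90 | 0 |
| C, dips and recovers | 80 | 80, 60, 50, 70, 80, 80 | 80 | 50 | −30 |
| D, improves | 70 | 70, then 80 throughout | 80 | 70 | 0 |

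The maximum gives A the same result as B, and C the same result as D. The minimum separates them. KPS is taken daily after infusion until discharge (footnote 7 of the schedule of assessments), and baseline is the last value before the infusion day (SAP 3.2.6). If the in-hospital scores count as post-baseline, the maximum of a steadily declining patient is simply the first score after infusion.

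**Step 4: how far apart the two statistics can lie.** Assumptions, not trial data: 30 patients, baseline 70 to 100, seven assessments, no recovery, and a 10-point drop with probability q/4 at the first assessment and q at each of the other six. Ignoring the floor of the scale:

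- Mean of (maximum − baseline) = −10 × q/4 = −2.5q.
- Mean of (minimum − baseline) = −10 × (q/4 + 6q) = −62.5q.
- Share falling 20 points or more, by the minimum = 1 − P(0 drops) − P(1 drop), where P(0) = (1 − q/4)(1 − q)^6 and P(1) = (q/4)(1 − q)^6 + (1 − q/4) × 6q(1 − q)^5.

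For q = 0.2, P(0) = 0.95 × 0.2621 = 0.249 and P(1) = 0.0131 + 0.3736 = 0.387, so the share is 1 − 0.249 − 0.387 = 0.364. Simulation (4,000 replicates) agrees with these formulas:

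| q | Mean change, maximum | Mean change, minimum | Fall of 20 or more, by maximum | Fall of 20 or more, by minimum |
|---|---|---|---|---|
| 0.1 | −0.3 | −6.3 | 0% | 12% |
| 0.2 | −0.5 | −12.5 | 0% | 36% |
| 0.3 | −0.7 | −18.7 | 0% | 60% |
| 0.5 | −1.3 | −31.3 | 0% | 90% |

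The 0% column follows from the set-up, since at most one 10-point drop can precede the first score. The change at the maximum is computed only to put both statistics on one scale; the SAP does not plan it.

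**Step 5: whether the by-visit table fills the gap.** Table 14.3.4.5 will give mean, median, standard deviation, minimum and maximum at each scheduled visit. A Week 8 minimum of 50 shows that at least one patient reached 50 at that visit. It does not show how many patients fell by 20 points or more at any time, nor whether the lowest patient at Week 5 is the lowest at Week 8. Under SAP 3.2.4 unscheduled assessments go to listings only. Protocol 5.3.1 includes KPS at the visit labelled unscheduled in Weeks 3 to 4, used when the first pembrolizumab dose is delayed, for instance for edema. If that visit is handled as unscheduled, its scores do not enter the by-visit table.

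**Step 6: the listing.** SAP 5.8.4 promises a KPS listing and SAP Section 5 says all collected data will be listed. The listing index in Section 10 has entries for vital signs and NANO but none for KPS.

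**The case against.** A reader might infer that the safety report conceals functional decline. The documents do not support that. The by-visit summaries come first in SAP 5.8.4, and their minimum would show a patient who had fallen to 40 at Week 8 if that was the lowest score at the visit. With about 30 patients planned, and fewer enrolled according to SAP Section 6, that row is informative. The primary safety endpoint is the frequency and severity of treatment-emergent adverse events, not KPS. Edema-related decline is captured in the severity, serious event, dose-limiting toxicity and special-interest tables, and NANO is tabulated by visit. All of this stands.

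Three other arguments should not be pressed:

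- **Attrition.** It is plausible that patients in steep decline stop attending, which would push later by-visit means upward, but neither document says so. Protocol 5.4 expects all treated patients to stay in follow-up. A minimum would also miss any decline that was never recorded.
- **Conflict with SAP 3.2.5.** That section permits worst-case displays without requiring them, so 5.8.4 does not contradict it.
- **A declining patient reported as having zero change.** The change in 5.8.4 is by visit, and no change to the maximum is planned.

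There is also a fair objection to the remedy. Protocol 1.1 puts survival at around 6 to 10 months, while follow-up runs to 104 weeks. In a single-arm study a worst-ever KPS will include decline from progression and before death. That is a reason to keep the by-visit changes beside it, not to report the best score instead.

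**Conclusion.** The point holds in limited form. The only per-patient KPS extreme in the SAP points the wrong way for a safety summary, most likely through wording carried over from vital signs, and no per-patient worst score is planned. The by-visit and adverse event tables still show deterioration but do not replace that score. The size is minor to moderate: one descriptive line, with no effect on any efficacy endpoint, analysis set, sample size or decision rule. The conclusion rests on reading KPS as higher-is-better, which follows from the eligibility floor, and on reading the sentence as a per-patient maximum. On the alternative reading the sentence is redundant and the gap is the same. The Step 4 figures illustrate direction only and do not predict this trial's results.

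**What to change.** In SAP 5.8.4, replace the maximum, or at least supplement it, with the minimum post-baseline KPS per patient and the change from baseline to that minimum. Use scheduled and unscheduled assessments, as SAP 5.8.2 does for laboratory values. Show the result as a separate row or panel of Table 14.3.4.5, because SAP 5.8 restricts the by-visit part to scheduled visits. A shift from baseline to worst in the SAP 5.1 categories would be a useful option. Leave the vital-signs sentence in 5.8.3 as it is. Add the promised KPS listing to the index in Section 10.

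The cost is one derivation and a small change to one table shell, from data already collected. A table note should say that the worst score reflects disease progression as well as treatment toxicity and is to be read with the by-visit changes.

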#### **5.8.5. NANO**

The number of participants and percentage in each category of the Neurologic Assessment in Neuro-Oncology (NANO) scale score.

A listing of NANO data will be generated.

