#### **8.4.5 Safety Analysis**

The full safety analysis set will include all patients who were administered at least one dose of the PVSRIPO. The safety of study-required pre-infusion procedures including catheter placement, will also be summarized.

Separate summaries will be prepared for the primary safety analysis set, which is patients who received PVSRIPO and  $\geq 1$  dose of pembrolizumab. Patients who received PVSRIPO alone will be summarized separately (secondary safety analysis).

Summaries of TEAE will begin at the time of PVSRIPO infusion. Adverse events considered related to screening or other pre-infusion procedures that are not SOC (eg, PV booster, biopsy prior to infusion, catheter placement without PVSRIPO infusion) will be summarized separately (screening data set).

All safety endpoints for patients receiving PVSRIPO and  $\geq 1$  dose of pembrolizumab may be summarized overall and by the number of pembrolizumab treatments received while on study (eg, 1, 2 to 3, 4 to 6, etc.).

Adverse events will be summarized by highest grade per patient and by attribution according to CTCAE v5.0, using the latest version of MedDRA preferred term as event category and MedDRA primary system organ class body term as Body System category. Unless otherwise stated, adverse events will be displayed in terms of frequency tables by treatment group by decreasing frequency. Each patient will be counted only once within each preferred term or system organ class. If a patient experiences more than one AE (or laboratory value) within a preferred term or system organ class for the same recording period, only the AE with the strongest relationship or the worst severity, as appropriate, will be included in the summaries of relationship and severity.

Events meeting the criteria for a DLT or SAE, leading to discontinuation, resulting in death, etc., will be reported in additional summaries. Changes from baseline over time and abnormal laboratory values, vital signs and NANO and KPS will also be reported.

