Lerapolturev 			X								
Pembrolizumab 					X	X	X	X	X		

Abbreviations: AE: adverse event; aPTT: activated partial thromboplastin time; ATT IgG: anti-tetanus toxoid immunoglobulin G; CBC with diff: Complete Blood Count with differential; CMP: Comprehensive Metabolic Panel; CT: computed tomography; DOR: duration of response; KPS: Karnofsky

performance status; LSQ: lymphocyte subset quantitation; MRI: Magnetic Resonance Imaging; NANO: Neurologic Assessment in Neuro-Oncology; PRO: patient-reported outcome; PT: prothrombin time; PV: poliovirus; SOC: standard of care; U: Unscheduled

- 1 At Screening Period 1, lab evaluations will occur first, followed by patients receiving their single PV booster vaccine.
- 2 Catheter placement and lerapoltrev infusion (+1 day window or extension as approved by Sponsor). Lerapoltrev infusion occurs only following confirmation of GBM at time of catheter placement or within 6 weeks of visit 3. If diagnosis of GBM is not confirmed/patient not infused, patient is a screen failure. Platelet count should be confirmed prior to catheter placement as well as at time of catheter removal and should remain consistent with inclusion criteria 11. Should the platelet count be less than 125 x 10^9/L on the day of catheter removal, a platelet transfusion should be administered and platelet count confirmed to be greater than 125 x 10^9/L prior to catheter removal.
- 3 Following Visit 4, all tests and procedures have a ±7-day window except for dose-limiting toxicity (DLT) assessment period for first 3 to 6 participants (21 days ± 3 days) post-first pembrolizumab infusion.
- 4 Questionnaires in support of PROs to occur at visits 2, 4, 6, 8 and then every 9-12 weeks per scheduled imaging visit follow-up.
- 5 Unscheduled (U): Visit occurs between visits 5 and 6 only if first dose of pembrolizumab is delayed from planned administration at visit 5. If first pembrolizumab infusion is delayed, the schedule of assessments shifts accordingly so the next visit occurs 3 weeks after the date of first pembrolizumab administration.
- 6 Includes height, weight, body surface area, vital signs (blood pressure, heart rate, respiratory rate, temperature).
- 7 Physical exam, neurologic exam with NANO and KPS daily after lerapoltrev infusion until day of discharge from hospital.

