### **3.2.4. Presentations by Study Visit**

When data are collected serially over time, individual data presentations may include by-study visit displays. By-study visit displays will only be summarized up to Week 104. Visits will be presented according to the nominal visit as obtained from the eCRF. If multiple observations are collected at a scheduled visit, the closest observation to the target day will be chosen. If two observations have equal distance from the target day but one is earlier and the other is later than the target day, the earlier observation will be chosen. Unscheduled assessments will be included in the listings.

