#### Safety

- 14.3.1.1 Overall Summary of Treatment-Emergent Adverse Events, Safety Set
- 14.3.1.2 Treatment-Emergent Adverse Events by System Organ Class, Preferred Term, and Greatest Severity, Safety Set
- 14.3.1.3 Treatment-Emergent Adverse Events by Preferred Term in Descending Frequency, Safety Set
- 14.3.1.4 Treatment-Emergent Adverse Events Related to Study Drug or Catheter by System Organ Class, Preferred Term, and Greatest Severity, Safety Set
- 14.3.1.5 Treatment-Emergent Adverse Events Related to Study Drug or Catheter by Preferred Term in Descending Frequency, Safety Set
- 14.3.1.6 Treatment-Emergent Serious Adverse Events by System Organ Class, Preferred Term and Greatest Severity, Safety Set
- 14.3.1.7 Treatment-Emergent Serious Adverse Events Related to Study Drug or Catheter by System Organ Class, Preferred Term, and Greatest Severity, Safety Set
- 14.3.1.8 Treatment-Emergent Dose Limiting Toxicities by System Organ Class, Preferred Term and Greatest Severity, Safety Set
- 14.3.1.9 Treatment-Emergent Adverse Events of Special Interest for Lerapoltrev by System Organ Class, Preferred Term, and Greatest Severity, Safety Set
- 14.3.1.10 Treatment-Emergent irAEs for Pembrolizumab by System Organ Class, Preferred Term, and Greatest Severity, Safety Set
- 14.3.1.11 Treatment-Emergent Adverse Events Leading to Discontinuation of Study Treatment by System Organ Class, Preferred Term, and Greatest Severity, Safety Set
- 14.3.4.1 Summary of Grade Shifts in Laboratory Abnormalities – Hematology, Safety Set
- 14.3.4.2 Summary of Grade Shifts in Laboratory Abnormalities – Chemistry, Pancreatic and Thyroid, Safety Set

- 14.3.4.3 Number of Participants with at Least One ALT, AST, or Total Bilirubin Above Upper Limit of the Normal Range Post-Baseline, Safety Set
- 14.3.4.4 Summary of Vital Signs by Visit, Safety Set
- 14.3.4.5 Summary of Karnofsky Performance Status by Visit, Safety Set
- 14.3.4.6 Summary of Neurologic Assessment in Neuro-Oncology Score by Visit, Safety Set

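### The SAP tabulates NANO only as category counts by scheduled visit, so within-patient worsening on NANO will be listed but not tabulated, and dropping the protocol's change from baseline is not recorded

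*SAP*

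**What the plan says.** SAP 5.8.5 describes the NANO summary in one incomplete sentence: "The number of participants and percentage in each category of the Neurologic Assessment in Neuro-Oncology (NANO) scale score". It adds "A listing of NANO data will be generated". SAP Section 10 has one NANO table, "14.3.4.6 Summary of Neurologic Assessment in Neuro-Oncology Score by Visit, Safety Set".

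Two general rules decide which scores enter that table. SAP 5.8 states "Safety summaries by visit will use scheduled visits up to Week 104". SAP 3.2.4 uses the nominal visit from the eCRF, sends unscheduled assessments to the listings, and adds "If multiple observations are collected at a scheduled visit, the closest observation to the target day will be chosen".

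More NANO data are collected than this table can use. Footnote 7 of the SAP's schedule of assessments has "Physical exam, neurologic exam with NANO and KPS daily after lerapoltrev infusion until day of discharge from hospital". NANO is also scored at the extra Week 3 to 4 visit, held when the first pembrolizumab dose is delayed (Protocol 5.3.1).

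Protocol 8.4.5 states: "Changes from baseline over time and abnormal laboratory values, vital signs and NANO and KPS will also be reported". SAP Section 6, which itemizes departures from the planned analyses, has no entry for NANO change from baseline.

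**The concern.** In a single-arm trial, each patient's own baseline is the main internal reference for a neurologic score. Patients may enter with deficits: the performance-status floor is a KPS of 70, so a category count after infusion mixes old deficits with new ones. Patients who decline and leave also drop out of later columns, which can make the distribution look stable or better.

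The period of most interest is poorly served. Post-infusion NANO is scored daily until discharge, but the by-visit rule keeps at most one value per scheduled visit. The Week 3 to 4 scores come from patients whose pembrolizumab was delayed, for edema among other reasons, and they may not reach the table at all.

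At stake is whether the report can state, from a planned table, how many participants became worse on NANO than they were at baseline. Protocol 7.4 centres the dose-limiting toxicity definition on neurologic events, so a reader of the safety results will want that number.

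**Working it through.** The plan states no figure here to reproduce. The check compares the sections, then asks what marginal counts can and cannot show.

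**Step 1. Within-patient comparison planned for each measure that Protocol 8.4.5 names**

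- Laboratory values (SAP 5.8.2): shift in grade from baseline to worst post-baseline value, using scheduled and unscheduled assessments.
- Vital signs (SAP 5.8.3): observed values and change from baseline at each visit, plus the maximum post-baseline value.
- KPS (SAP 5.8.4): the same as vital signs.
- NANO (SAP 5.8.5): category counts and a listing. No change, shift or worst value.

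NANO is the only one of the four without a within-patient comparison.

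**Step 2. Is the omission declared?** SAP Section 6 lists dropped analyses in detail, including the subgroup analysis by baseline NANO score, but not NANO change from baseline. Protocol Section 8 gives the SAP precedence where the two differ, so the protocol's provision lapses without a stated reason.

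**Step 3. Does another provision supply it?** SAP 3.2.5 permits worst-case displays that use scheduled and unscheduled data, but only as something displays may include. Neither SAP 5.8.5 nor the table list invokes it for NANO. Protocol 8.4.4.4 brings unscheduled data into the safety analyses and limits only by-visit descriptive statistics to scheduled visits, so a worst-value NANO table would be consistent with it. The KPS maximum does not help: eligibility sets a minimum KPS, so higher is better and the maximum post-baseline value is each patient's best score.

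**Step 4. Can by-visit counts show worsening?** Take n patients and two categories, better and worse. Let a be the number in the better category at baseline and b the number there at a later visit. The number W who moved from better to worse satisfies

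max(0, a − b) ≤ W ≤ min(a, n − b).

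With the planned n = 30 and assumed splits:

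- a = 15, b = 15: max(0, 0) = 0 and min(15, 15) = 15, so W is 0 to 15.
- a = 20, b = 20: max(0, 0) = 0 and min(20, 10) = 10, so W is 0 to 10.
- a = 20, b = 18: max(0, 2) = 2 and min(20, 12) = 12, so W is 2 to 12.

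The splits are illustrations, not trial data. The same published counts fit no worsening or worsening in half the patients.

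**Step 5. Which collected scores can enter the table?** Protocol 5.3 places the daily post-infusion assessments under Visit 4, so SAP 3.2.4 keeps at most one of them. The Week 3 to 4 visit is labelled unscheduled but has its own column in the schedule of assessments and protocol-specified NANO. Whether it counts as scheduled depends on how the eCRF names it, which the documents do not say. Its exclusion is possible but not established.

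**The case against.** The strongest reply is that little is lost. SAP 5.8 and 5.8.5 list every NANO value by participant, and unscheduled assessments are included in the listings. About 30 patients were planned and SAP Section 6 says the full number was not enrolled, so each course can be read by eye. Neurologic harm is also tabulated elsewhere: treatment-emergent events by greatest severity (Table 14.3.1.2), dose-limiting toxicities (14.3.1.8), and cerebral and peritumoral edema as events of special interest (14.3.1.9). Adverse events are collected continuously, and their definition in Protocol 7.1 leaves out fluctuation in existing conditions that does not worsen. All of this stands, and it limits the point to one descriptive table.

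The sentence in Protocol 8.4.5 is also loosely built. One could read the change from baseline as separate from the measures listed after it. But the SAP gives change or shift to the other three, so the natural reading covers NANO too.

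Attrition affects any by-visit table, including the KPS one, and SAP Section 9 requires missing observations to be noted. That is fair. It makes attrition visible but does not show who worsened.

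Three stronger readings are tempting and unsupported:

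- That neurologic worsening will go unreported, or that the plan cannot count it. The listings and adverse event tables contradict this.
- That NANO is the trial's designated measure of edema. Protocol 7.5.2 captures edema through graded events on edema-specific forms, and Protocol 8.4.6.1 uses NANO to explore neurologic function as a correlate of response.
- That a known share of deficits is missed. With visits 21 days apart and uniform onset, a deficit of d days meets a visit with probability d/21: 7/21 = 33% and 14/21 = 67%. The 7 and 14 days are assumptions, the documents give no durations, and early assessments are closer together than 21 days.

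**Conclusion.** The point holds in a limited form. As written, the SAP tabulates NANO only as category counts at scheduled visits. Within-patient worsening on NANO will be available in a listing but in no summary, and the departure from Protocol 8.4.5 is not recorded in SAP Section 6. This rests on the text of SAP 5.8, 5.8.5, 3.2.4, Section 6 and Section 10, and on reading the Protocol 8.4.5 sentence as covering NANO.

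The size is modest. No primary endpoint or adverse event table is affected. What is missing is one number, the participants worse than baseline on NANO, which by-visit counts cannot supply: under the assumed 15/15 split the range is 0 to 15 of 30. The documents do not allow an estimate of how many actual cases the by-visit table would leave out. It is worth correcting because the data are already collected and the SAP applies a better method to laboratory values.

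**What to change.** Add to SAP 5.8.5, and to the table list, a shift table from baseline to worst post-baseline NANO score, with the number and percentage of participants worse than baseline. Use all scheduled and unscheduled assessments, naming the daily post-infusion scores and the Week 3 to 4 visit. Model it on the laboratory shift in SAP 5.8.2 and use the baseline definition in SAP 3.2.6. State which direction of the score is worse, since the SAP does not. Keep Table 14.3.4.6 as supportive.

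If the table is not added, SAP Section 6 should at least record that NANO change from baseline is dropped, and why.

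The cost is a short text change and one table, with no new data or visits. The downside is that a worst-value display also captures decline from tumor progression, which a footnote can state.
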